9.0 MONITORING UNTOWARD EFFECTS ASSOCIATED WITH OR RESULTING FROM STUDY

Site research staff must first follow both the UNC IRB and their own IRB's procedure for reporting and managing untoward effects.

There are three types of untoward effects to be identified: 1) those related to the participant, 2) those related to the study staff, and 3) those related to the neighborhood/community (*if applicable*).

First, the study will catalogue any untoward effect related to the participant. Reporting is required for occurrences including social harms, psychological distress, and serious life-threatening events such as suicide attempts. These may be immediately apparent to the study staff, such as the participant's emotional upset state requiring referral for counseling; or they may be delayed and reported later to study staff, such as physical harm to an individual for having participated in the study. Study staff will notify the UNC/Duke teams via secure email with a subject line stating that immediate response is necessary. Study staff will be briefed with best practices and trainings on the scope of possible untoward effects and how to report events.

Second, study staff may encounter untoward events during sessions that personally affect them. Training and guidance will seek to minimize this risk. Nonetheless, an assessment of the cost of conducting this study must include cataloguing these events as well. The UNC/Duke team will be notified of these events so that they may be immediately addressed, evaluated, and then modify guidance or expanded to minimize similar risk to other study staff.

Third, a critically important area that any community-based study intends to evaluate is the impact, including untoward effects, of the project on the community. This will be done informally for this protocol with untoward events being reported to the protocol team.

All untoward effects/adverse events/unanticipated problems will also need to be reported to the UNC IRB if they meet all three of the following criteria:

"Unanticipated problems involving risks to subjects or others" (UPIRSO) refers to any incident, experience, or outcome that:

- 1) is unexpected (in terms of nature, severity, or frequency) given (a) the research procedures that are described in the protocol-related documents, such as the IRB-approved research protocol and informed consent document; and (b) the characteristics of the subject population being studied;
- 2) is related or possibly related to a subject's participation in the research; and
- 3) Suggests that the research places subjects or others at a greater risk of harm (including physical, psychological, economic, or social harm) than was previously known or recognized.

Events that meet the criteria for an UPIRSO and are also serious adverse events should be reported to the UNC IRB within one (1) week of the investigator becoming aware of the event. Any other events that meet the criteria for a UPIRSO should be reported to the IRB within two (2) weeks of the investigator becoming aware of the problem.

If the report cannot be completed in its entirety within the required time period, a preliminary report should be submitted. The report should be amended once the event is resolved and/or more information becomes available.

10.0 STATISTICAL/ANALYTIC CONSIDERATIONS

10.1 Overview of analytic strategy

10.1.2 Technical Pilot

To evaluate the functionality, technical performance, errors and bugs encountered, overall experiences using Tough Talks, and provide feedback for further refinement.

10.1.3 RCT

Conduct a combined efficacy/effectiveness trial to compare the intervention delivered online, in the clinic, or SOC clinic disclosure messaging. The primary outcome of HIV viral suppression will be assessed at six months. We will also assess intervention efficacy on a panel of self-reported outcomes including CAI, STI infections, disclosure behaviors, intentions and self-efficacy assessed at baseline, 3 months, and 6 months. Cost effectiveness of both intervention arms will also be assessed.

The primary analysis will be based on intention-to-treat principles, where all participants are assumed to have followed their randomized assignment; secondary analyses will account for observed intervention completion. Additionally, we will develop a mathematical model to estimate secondary HIV transmissions and potential transmissions averted as a result of the intervention's effect on viral suppression and CAI with susceptible partners.

10.2 Power Estimates

10.2.2 Technical Pilot Power Considerations

Power is not a concern for the technical pilot as it is performed to collect feedback from a small number of members from the target population about the functionality of the near final version of the intervention.

10.2.3 RCT Power Considerations

Power and sample size. The sample size calculation is based on the primary aim examining a change in the probability of **viral load suppression** from baseline to six months of follow-up between the standard of care arm and each of the two intervention arms. Using data from previous work, we estimate the probability of viral load suppression to be 0.66 in each of the three trial arms at baseline, and a change in this probability to 0.88 in each of the two intervention arms at six months of follow-up. Assuming this absolute change of 0.22, a two-sided alpha level of 0.05, and 15% loss to follow-up over the six-month study period, we estimate we will need 66 participants in each of the 3 study arms (n=198) to achieve 80% power to detect this change in the probability of viral load suppression between SOC and the two intervention arms. While our sample size is not powered to detect a difference between the two intervention arms, precise estimates of the efficacy for each arm are critical for subsequent costing analyses.

Power calculations were performed using PASS v.13 software (NCSS, LLC. Kaysville, Utah).

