4.0 SELECTION AND ENROLLMENT OF PARTICIPANTS

4.1 Inclusion Criteria

Inclusion Criteria for All Aims

- Age 16-29 years
- Assigned male sex at birth
- Born male and male-identified
- Able to understand, read, and speak English

Additional Criteria for Technical Pilot:

- Reports ≥ 1 episode of CAI with a male partner in past 6 months
- HIV-positive (self-report)

Additional Criteria for RCT:

- HIV-positive (medical chart review)
- Viral Load measure within 12 months of screening date (assessed by chart review, blood draw, or shared by participant via video teleconferencing or Qualtrics)
- Owns and has reliable access to a smartphone or tablet
- Has reliable internet access
- Reports ≥1 episode of anal sex with a male partner in past 6 months (self-report) OR reports STI diagnosis (urethral/rectal gonorrhea or chlamydia or syphilis) in the last six months (self-report OR medical chart review)

As this is a minimal risk study, we will seek a waiver of parental consent for YMSM under age 18 (see Human Subjects section).

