4.2 Exclusion Criteria

Exclusion Criteria for All Aims:

- Under 16 years of age
- Over 29 years of age
- Assigned female at birth
- HIV negative
- Reports 0 episodes of anal sex with a male partner in the last 6 month AND reports no new STI diagnosis (urethral/rectal gonorrhea or chlamydia or syphilis) in last 6 months.
- Currently enrolled in another HIV behavioral intervention study; previous or future enrollment in another HIV behavioral intervention study is permissible, as is participation in any standard of care intervention(s) within the clinical study site.

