Those randomized to the in-clinic condition (Arm 2) at this visit will download the Tough Talks app onto their personal mobile phone or tablet, have their unique App ID recorded by study staff, set up their preferred email login and password information, and immediately begin using the program. At this in-person or remote visit, they will complete both Modules 1 and 2, which includes completion of four virtual reality practice scenarios. These scenarios will be conducted with the assistance of research staff controlling the avatar responses (e.g. clinic-assisted sessions). For the remote visits, staff will do this privately while on video teleconference. During the in-person visits, the staff would control the avatar responses from a separate room. After completion of both Modules 1 and 2 of the program, participants will schedule their follow-up visit for approximately two weeks and receive information on how to contact study personnel for any technical issues when using the first half of the program at home. For those completing the modules remotely, they will receive a list of national resources for mental health support. Their two-week visit can happen anywhere during week 2 or week 4 of the study period. At their follow-up visit, participants will complete the second half of the program (Modules 3 and 4), which also includes completion of the virtual reality practice scenarios as described above (clinic-assisted sessions). Research staff will also be available to troubleshoot with participants in person or for the remote visits they will be on video teleconference and available via text if need be.

Those randomized to the SOC control arm (Arm 3) at this visit will receive an informational, paper or electronic packet of information on disclosure based on available CDC guidance.

Participants will be allowed to enroll in-person at the site or remotely via Zoom or another HIPPA compliant system. All participants who enroll remotely will be asked to download the necessary app to aid the enrollment process. They will receive all forms via text or email. Participants who enroll from across the country (in states where there are no SRVs) will be assigned to an SRV by region. For example, the Houston site staff may enroll the participants from western states, whereas the Tampa site staff may enroll participants from the southern states. The regional division of enrollments is subject to update

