10.3.3 RCT Primary Analysis Plan

The study is a multi-site randomized 3-arm parallel group, longitudinal trial. The primary analysis will be based on intention-to-treat principles where we assume that all participants have followed their randomized assignment. The primary outcome is the probability of viral load suppression at six months, defined as less than the lower limit of detection as per the laboratory at each clinical site. At baseline, the most recent viral load will be abstracted from participants' medical records, within a specified time window (per trial eligibility criteria). At six months, participants' most recent viral load will be abstracted if one is available in the 2-month window prior to the six-month follow-up visit; if none is available within that window, a blood draw will be done for the study to ascertain viral load, or participant can have viral load measure as part of normal care within three months after six-month visit. We will use a binomial regression model (with identity link) for the risk difference (RD) in 6-month viral suppression, comparing each of the intervention groups with the SOC group. Due to random assignment, we expect that the probability of viral suppression at baseline will be balanced between the intervention and control groups. However, if baseline differences occur by chance, we will use inverse probability of treatment weights to correct imbalances in baseline viral suppression. Additional baseline covariates may be included in the model to increase the precision of treatment effects. The treatment weights may be combined with censoring weights if loss to follow-up exceeds 15% or if there is evidence of differential censoring by treatment group.

All analyses will be conducted using R (R Foundation for Statistical Computing, Vienna, Austria).

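### The 80% power in 10.2.3 rests on an unstated six-month SOC rate of 0.66, and 10.3.3 adjusts for baseline suppression only if a chance imbalance is seen

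*Combined protocol and SAP*

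**What the plan says.** Section 10.2.3 describes the aim as a comparison of SOC with each intervention arm. Its starting point is that "we estimate the probability of viral load suppression to be 0.66 in each of the three trial arms at baseline". Both Tough Talks arms are then taken to reach 0.88 by month six. With the resulting 0.22, two-sided alpha 0.05 and 15% loss to follow-up, it arrives at 66 per arm (198 in total) "to achieve 80% power to detect this change in the probability of viral load suppression between SOC and the two intervention arms". It attributes the rates to previous work. It gives no six-month rate for SOC.

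Section 10.3.3 (primary analysis) specifies a "binomial regression model (with identity link) for the risk difference (RD) in 6-month viral suppression", with each intervention arm set against SOC. Baseline suppression is expected to balance through randomisation. Inverse probability of treatment weights are to be used if it turns out unbalanced by chance, and other baseline covariates may be added for precision.

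The baseline value exists for everyone, because RCT eligibility in 4.1 requires a "Viral Load measure within 12 months of screening date".

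**The concern.** The planned test compares two six-month rates, so its power depends on the six-month SOC rate. Section 10.2.3 supplies a within-arm change and treats it as the between-arm difference. The two are equal only if SOC does not move. A reader of 10.2.3 cannot tell that the 80% carries this condition, or on what evidence.

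Some features of the plan make a fixed 0.66 uncertain. The baseline reading may be 12 months old at screening. The final one may come late, since a "participant can have viral load measure as part of normal care within three months after six-month visit". The two can therefore lie about 12 + 6 + 3 = 21 months apart. On other programmes, 4.2 says that "previous or future enrollment in another HIV behavioral intervention study is permissible". SOC participants also "will receive an informational, paper or electronic packet of information on disclosure based on available CDC guidance" (5.1).

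If SOC improves and the intervention rate stays at 0.88, a null result could be read as failure of Tough Talks when the trial had limited power for the smaller difference. The plan already holds a tool against this, adjustment for baseline suppression, but leaves its use to a decision made after looking at the data.

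**Working it through.** **Inputs.** Rates 0.66 and 0.88, two-sided alpha 0.05, 80% power and 15% loss come from 10.2.3. Evaluable per arm: 66 × 0.85 = 56.1, so 56. Section 5.4.3 agrees, giving 112 retained in the two intervention arms.

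**Reproducing the plan's figure.** Pooled two-proportion formula, with mean rate p̄ = (0.66 + 0.88)/2 = 0.77:

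n = [1.960 × √(2 × 0.77 × 0.23) + 0.842 × √(0.66 × 0.34 + 0.88 × 0.12)]² / 0.22² = 56.25 evaluable per arm.

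56.25 / 0.85 = 66.2, the plan's 66. (Rounding up to 57 before dividing gives 68, an immaterial gap.)

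**Power at 56 per arm.** Power = Φ{[difference − 1.960 × √(2p̄(1 − p̄)/56)] / √([p₁(1 − p₁) + p₂(1 − p₂)]/56)}. For 0.66 vs 0.88 this is Φ[(0.22 − 1.960 × 0.0795)/0.0768] = Φ(0.835) = 79.8%.

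**Same formula, other six-month rates (unadjusted):**

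| SOC | Intervention | Power |
|---|---|---|
| 0.64 | 0.88 | 85.5% |
| 0.66 | 0.88 | 79.8% |
| 0.68 | 0.88 | 73.0% |
| 0.70 | 0.88 | 65.1% |
| 0.72 | 0.88 | 56.4% |
| 0.70 | 0.92 | 85.3% |

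The SOC values are illustrative, since the documents give none at six months. For scale, a 4-point SOC gain means a net 0.04/0.34 = 12% of those unsuppressed at baseline becoming suppressed; the plan assumes a net 0.22/0.34 = 65% in the intervention arms.

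**Check against the planned kind of test.** Exact enumeration of an unadjusted Wald test of the risk difference gives 82.1% at SOC 0.66 and 67.6% at SOC 0.70. That is about 2.5 points above the approximation, with the same pattern.

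**Value of always adjusting for baseline suppression.** Simulation, 56 per arm, 40,000 trials per setting, standardised risk difference with a Wald test. The baseline to six-month correlation is assumed to be 0.2 to 0.4, because the documents give none.

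- SOC 0.66 vs 0.88: about 82% unadjusted, 83–88% adjusted.
- SOC 0.70 vs 0.88: about 68% unadjusted, 69–75% adjusted.
- No true difference: a false finding of benefit in about 2.7–2.8% of trials, with or without adjustment (nominal 2.5%).

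**Why not simply add the covariate to the identity-link model.** At SOC 0.70 and correlation 0.4, six-month suppression among SOC participants suppressed at baseline is 0.70 + 0.4 × √(0.70 × 0.30 × 0.34/0.66) = 0.83. Adding a constant effect of 0.18 gives 1.01, which is above 1, so an additive model may reach its boundary.

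**The case against.** The strongest reply is that nothing is miscalculated. Section 10.2.3 frames the comparison as between arms. With all arms at 0.66 at baseline, a difference in change equals a six-month difference, and 66 per arm reproduces as exactly that contrast. Since the section gives a change only for the intervention arms, a flat SOC rate is easily inferred. All of this stands. A reader might infer that the trial was sized on the wrong quantity; the documents do not support that.

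A reader might also infer that true power is about 65%. That needs SOC to gain 4 points while intervention stays at 0.88. Most of the features listed above do not point there. The long interval between readings and the freedom to join other studies apply to every arm, and the 21 months pairs the oldest permitted baseline with the latest permitted final reading. Only the disclosure packet is specific to SOC, and nothing in the documents says that it raises suppression. A shared 4-point rise gives 85.3%, and a fall in SOC also raises power. The source of 0.66 and 0.88 cannot be seen, so whether 0.88 already includes improvement under usual care is unknown.

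Finally, 10.3.3 already allows weights and covariates. It does, but conditionally or optionally, so the precision is neither assured nor fixed in advance. The gain is modest if an old baseline reading correlates weakly with the final one: at correlation 0.2 it is only 1 to 2 points.

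**Conclusion.** The point holds in a limited form. The stated 66 per arm and 80% are arithmetically sound, conditional on SOC remaining at 0.66 at six months. That condition is implied, not stated, and no basis for it is given. This part is mainly missing detail. The evidence does not show that the trial is underpowered and does not justify a larger sample.

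The part that would improve the analysis itself is the conditional baseline adjustment. Making it unconditional uses data already required, leaves the false-positive rate essentially unchanged, and adds roughly 1 to 7 points of power across the two SOC rates simulated. These gains rest on 56 evaluable per arm, an intervention rate of 0.88 and the assumed correlation of 0.2 to 0.4. The change should be made, but the plan is workable without it.

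**What to change.** 1. **Section 10.3.3 (primary analysis).** Pre-specify that each six-month risk difference against SOC is adjusted for baseline viral suppression in every case. Name one method: a standardised (g-computation) risk difference from a logistic model, or treatment weights that always include baseline suppression. Use a variance estimate that accounts for the adjustment. Do not enter the covariate in an additive identity-link model.

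2. **Section 10.2.3.** State that the calculation takes 0.66 under SOC and 0.88 under intervention at six months, cite the source within the previous work, and say that 80% is conditional on these rates. Add one line of unadjusted power with 0.88 held: 85.5% at SOC 0.64, 73.0% at 0.68, 65.1% at 0.70 and 56.4% at 0.72, with 85.3% for 0.70 vs 0.92. Label these as scenarios.

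**Cost.** Wording in two sections and slightly more analysis work. No new data are needed and n = 198 stays. The drawback is that the stated power becomes visibly conditional.

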10.3 Statistical Analysis Plan

10.3.2 Technical Pilot Analysis Plan

All data collected during Phase 1, the Technical Pilot, will be qualitative in nature and therefore not have a statistical analysis plan.

10.3.3 RCT Primary Analysis Plan

The study is a multi-site randomized 3-arm parallel group, longitudinal trial. The primary analysis will be based on intention-to-treat principles where we assume that all participants have followed their randomized assignment. The primary outcome is the probability of viral load suppression at six months, defined as less than the lower limit of detection as per the laboratory at each clinical site. At baseline, the most recent viral load will be abstracted from participants' medical records, within a specified time window (per trial eligibility criteria). At six months, participants' most recent viral load will be abstracted if one is available in the 2-month window prior to the six-month follow-up visit; if none is available within that window, a blood draw will be done for the study to ascertain viral load, or participant can have viral load measure as part of normal care within three months after six-month visit. We will use a binomial regression model (with identity link) for the risk difference (RD) in 6-month viral suppression, comparing each of the intervention groups with the SOC group. Due to random assignment, we expect that the probability of viral suppression at baseline will be balanced between the intervention and control groups. However, if baseline differences occur by chance, we will use inverse probability of treatment weights to correct imbalances in baseline viral suppression. Additional baseline covariates may be included in the model to increase the precision of treatment effects. The treatment weights may be combined with censoring weights if loss to follow-up exceeds 15% or if there is evidence of differential censoring by treatment group.

All analyses will be conducted using R (R Foundation for Statistical Computing, Vienna, Austria).

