3.3 Study Randomization, Stratification, or Description of Non-Random Assignment Procedures

Technical Pilot: Participants will be recruited from UNC-Chapel Hill. We will enroll 8-16 participants. After participants are consented, they will complete a web-based computer assisted survey instrument (CASI) using Qualtrics software. Participants will be randomized to either use Modules 1 and 2 or Modules 3 and 4. Participants will receive a short orientation to the program before use. Participants will be provided with a notebook to take notes on each activity, as well as take a survey on each activity. At the end of each module, participants will do a short qualitative semi-structured interview. At the end of the second module, they will take a post survey. They will receive \$75 for their participation in this aim of the study. Participants can choose to re-enroll and complete the other two Modules of Tough Talks as well.

RCT: Participants will be recruited from across the country. We will enroll a total of 198 participants. After participants are consented, they will complete a baseline web-based computer assisted survey instrument (CASI) survey using Qualtrics software and be randomized in a 1:1:1 fashion into one of three arms: 1) the Tough Talks fully-online intervention, 2) the Tough Talks clinic-based intervention or 3) the SOC control condition, based on a randomization sequence developed by UNC and administered through REDCap. The randomization sequence will be stratified by study site. Participants may enroll in-person or remotely via video teleconferencing system.

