10.3.3 RCT Secondary Analysis Plan

The occurrence of CAI with a potentially susceptible partner in the last three months will be assessed at baseline, three-months, and six-months following the intervention. At each time point, participants will complete the web-based CASI survey that will include items on sexual risk behaviors over the prior three months. These items will ask about frequency of insertive and receptive anal intercourse, condom use, and number and HIV status of partners. CAI with a potentially susceptible partner will be defined as ≥ 1 act of condomless anal intercourse with a partner who is not known to be HIV-positive. To assess intervention effect at the time point of primary interest (six months), we will use a binomial regression model (with identity link) for the RD in any CAI with a susceptible partner (vs. none) at six months, comparing the intervention groups to the control group. Similar to viral suppression, we expect that the probability of CAI with a susceptible partner will be similar for intervention and control groups at baseline. We will use inverse probability of treatment weights to correct any imbalances in baseline CAI with a susceptible partner. In addition, baseline covariates may be included in the model to improve precision of treatment effects. Censoring weights may also be included if loss to follow-up exceeds 15% or if there is evidence of differential censoring by treatment group.

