In addition to the main six-month CAI outcome (any CAI with a potentially susceptible partner in the last 3 months), we will conduct a separate analysis in which “potentially susceptible partner” is defined as a partner who is not known to be HIV-positive or taking HIV medications (including PrEP). Additionally, we will compare the intervention and control arms with respect to the number of CAI acts in the last three months according to partner HIV and PrEP status (known HIV-positive, HIV-negative and not on PrEP, HIV-negative and on PrEP, unknown HIV status). Finally, linear mixed models will be fitted to all continuous outcome measures (i.e., self-regulation, self-efficacy to disclose, disclosure outcome expectations, consequences of disclosure, and intentions to disclose) to estimate the relative change in mean response from baseline to 6 months between intervention and SOC groups. Before fitting all models we will look for balance between treatment arms to assess the success of randomization, and we will adjust for possible confounding variables to improve precision and validity where needed. In the event that loss to follow-up is differential across treatment arms, we will employ inverse probability weighting to correct for this selection bias. We will test hypotheses using the likelihood ratio test, and goodness-of-fit among models will be assessed using the likelihood-ratio test, AIC and BIC criteria. Intervention completion and acceptability will be assessed at 1 month, and sensitivity analyses will evaluate how our findings for primary outcomes are influenced when we account for observed intervention completion.

Transmission Model

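### Baseline adjustment of the primary risk difference depends on an undefined chance imbalance, has no assigned variance or test, and no analysis model names site, the randomisation stratum

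*Combined protocol and SAP*

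**What the plan says.** The primary model in section 10.3.3 (RCT Primary Analysis Plan) is a binomial regression with identity link for the RD, comparing each intervention arm with SOC. Baseline suppression enters only through a condition: "if baseline differences occur by chance, we will use inverse probability of treatment weights to correct imbalances in baseline viral suppression". Of other variables the section says "Additional baseline covariates may be included in the model to increase the precision of treatment effects", and it names none. It also allows the treatment weights to be combined with censoring weights. It gives no standard error, confidence interval or test for the RD, weighted or not.

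The secondary plan (also numbered 10.3.3) repeats the pattern for condomless anal intercourse (CAI): "We will use inverse probability of treatment weights to correct any imbalances in baseline CAI with a susceptible partner". It then says that after a look at balance "we will adjust for possible confounding variables to improve precision and validity where needed", and adds "We will test hypotheses using the likelihood ratio test". That last sentence does not say which models it covers.

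Sections 3.3 and 5.3 state the design: "The randomization sequence will be stratified by study site". Remote participants also belong to a site stratum: "Participants who enroll from across the country (in states where there are no SRVs) will be assigned to an SRV by region" (section 5.1, which adds that the regional division may change). Eligibility for the RCT requires a "Viral Load measure within 12 months of screening date" (section 4.1), so a baseline value should exist for everyone randomised.

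**The concern.** Two analysts could follow this text and reach different results from the same data. One might weight and use an ordinary robust standard error. Another might bootstrap the weights. A third might decide that the arms look balanced and not weight at all. All three estimates are unbiased, but their precision and error rates differ.

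The likelihood ratio test adds a specific problem. A model fitted with estimated weights does not have an ordinary likelihood, so the statistic does not have its usual reference distribution. This is the only test that section 10.3.3 names, and it stands in the same secondary plan as the weighted CAI model.

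Site determined the allocation strata, yet a reader cannot tell whether it will be in any model.

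**Working it through.** **Inputs from the documents.** Section 10.2.3: suppression 0.66 at baseline in all arms, 0.88 at six months in the intervention arms, two-sided alpha 0.05, 80% power, 15% loss, 66 per arm. SOC at six months is taken as 0.66, which the stated change of 0.22 implies. Evaluable per arm: 66 × 0.85 = 56.1, so 56; section 5.4.3 likewise gives 112 for two arms.

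**Assumption.** The correlation φ between baseline and six-month suppression is not in the documents. I use 0 to 0.5. The low end is plausible because the baseline viral load may be up to 12 months old.

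**1. The plan's own figure.** With pooled variance, n = (1.960 × √(2 × 0.77 × 0.23) + 0.842 × √0.33)² / 0.22², where 0.33 = 0.66 × 0.34 + 0.88 × 0.12. This gives 57 evaluable per arm. 57 × 1.15 = 65.6, or 66; 57 / 0.85 = 67.1, or 68. The stated 66 is reproduced within tolerance. Power at 56 per arm is 79.8% (pooled). Unpooled, SE = √(0.33/56) = 0.0768, and Φ(0.22/0.0768 − 1.96) = 81.8%.

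**2. How often the trigger fires.** If any non-zero difference counts, weights are skipped only when all three arms have equal baseline counts. With b(k) the binomial(66, 0.66) probability, Σ b(k)³ = 0.62%. The trigger fires in 99.4% of trials, and the rule then loses 0.05 points of power or less against always adjusting.

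**3. What the variance does.** With weights on baseline suppression only, the weighted proportion in arm a is Σ_b w_b p_ab, where w_b is the share of all 168 evaluable participants in baseline stratum b.
- A variance that accounts for estimated weights is Σ_a Σ_b w_b² p_ab(1 − p_ab)/n_ab + w_1 w_0 (d_1 − d_0)²/168, where d_b is the RD in stratum b.
- A weights-fixed sandwich takes residuals around the arm mean, so it still counts the between-stratum variation that weighting has removed.

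Power by simulation (200,000 or more three-arm trials per setting):

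| φ | Unadjusted | Variance accounts for weights | Weights-fixed robust SE |
|---|---|---|---|
| 0 | 82% | about 81% | about 82% |
| 0.2 | 82% | 82-83% | 82% |
| 0.3 | 82% | 84-85% | 82-83% |
| 0.5 | 82% | 88-91% | 84-85% |

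The ranges cover the same φ or the same odds ratio in the intervention arms, and use or not of a small-sample correction. With that correction, null error in the middle column is 5.2-5.4%, against 5.6-5.7% unadjusted. The deficit at φ = 0 comes mostly from the correction.

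**4. Likelihood ratio test on a weighted RD.** Unstabilised weights average 3 with three arms, so the statistic is about three times too large. It is in effect compared with 3.84/3 = 1.28, and P(χ²₁ > 1.28) is about 26%. Simulated null error for φ from 0.2 to 0.5 is 20-26% with unstabilised weights and about 3-5% with stabilised weights.

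**5. Site.** With six unequal sites (assumed 60/45/36/27/18/12) and a site log-odds SD of 0 to 0.6, adding site to the weights changes power by −0.2 to +0.9 points. Omitting it is at most slightly conservative (null error 4.5-4.8% at SD 0.6).

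**6. Where to put the covariates.** Adding baseline suppression and six sites to the identity-link binomial model failed (no convergence, or fitted values outside 0 to 1) in 70-90% of simulated trials at 0.66 versus 0.88. The fits used Python; R may differ in degree.

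**The case against.** The strongest reply is that the conditional wording does almost no harm. Taken literally it means adjusting nearly always, and step 2 confirms this. A reader might infer that the trigger itself wastes power. It would with a coarse cut-off: requiring a gap above 10 points would lose up to 4.9 points of power at φ = 0.5. But the plan states no cut-off, so that loss cannot be charged to it.

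The gain also rests on an unknown φ. In a check of the full method (weights on baseline and site, bootstrap, 1,500 trials), power adjusted versus unadjusted was 82.1% versus 83.8% at φ = 0 and 79.5% versus 80.4% at φ = 0.2, both without site effects. With site SD 0.3 it was 84.2% versus 83.3% at φ = 0.3 and 89.5% versus 80.9% at φ = 0.5. Monte Carlo error on each figure is about 1 point (√(0.82 × 0.18/1500) = 0.010). At low φ the change is neutral or slightly costly. This stands, and the gain should not be called free.

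A reader might infer that the primary test has 20-26% type I error. The documents do not support that. It would require the secondary plan's test sentence to govern the primary RD, and unstabilised weights; neither is stated. Nor is it right that the plan names no test at all, or that it excludes site: a test is named in the secondary plan, and unnamed covariates are permitted.

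Finally, a reader might suspect a choice between adjusted and unadjusted results after both are seen, which would put null error at about 6.6-8.1%. The stated trigger depends on baseline data only, so the plan does not provide for this. It simply does not fix the rule tightly enough to exclude it.

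**Conclusion.** The point holds as a gap in the primary analysis that should be closed before outcomes are seen. It is not an error that biases the RD or undermines the sample size. What is unspecified is what counts as imbalance, which variance and test apply to the primary RD, and whether site is adjusted for. The variance matters most. Treating the weights as fixed gives away most of the available gain: about 1 to 2 points of power at φ = 0.3 and 4 to 6 at φ = 0.5. There is nothing material to gain at φ = 0.2 or below.

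The likelihood ratio test is unsuitable for any weighted model, including the weighted CAI analysis if it is meant to apply there. Site is worth about 1 point at most; the reason to include it is that the analysis should follow the design. The sizes rest on the plan's 0.66 and 0.88, 56 evaluable per arm, and the assumed φ and site effects.

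**What to change.** In the primary plan, delete the imbalance condition and specify the following.

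- **Estimator.** Whatever the observed balance, estimate the marginal RD for each intervention arm versus SOC, adjusted for baseline suppression and for site as recorded at randomisation. Use either stabilised weights from one multinomial logistic model of arm, or a standardised logistic outcome model; choose one. Do not add these covariates to the identity-link binomial model.
- **Small sites.** Fix a pooling rule before outcomes are seen, for example merging any site with fewer than 15 randomised into the smallest remaining site.
- **Inference.** Use Wald tests and 95% confidence intervals with a variance that accounts for the adjustment, such as a bootstrap within arm (2,000 resamples) that re-estimates all weights each time, including any censoring weights. Do not resample within arm-by-site cells: null error there was 7.3-7.9%, against 4.8% within arm.
- **Details.** Say whether treatment weights are fitted on all randomised or only evaluable participants, and what is done when a resample leaves an arm-by-site cell empty (about 0.3% of resamples in the check).
- **Covariates.** Name any further covariates or delete the option.
- **Sensitivity.** Keep the unadjusted RD.

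In the secondary plan, do the same for CAI with baseline CAI, and restrict the likelihood ratio test to unweighted models.

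The cost is SAP wording and a few lines of R before outcome data are analysed. No new data are needed, and neither the sample size nor the marginal RD as the target changes. The downside is up to about 1 point of power if baseline suppression turns out not to be prognostic.
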